7.3.2 Exclusion Criteria

A person will be excluded from the study if they have:

- Have taken part in another clinical research study within the last 14 days.
- Are currently habitual wearers of toric contact lenses.
- Have worn any rigid contact lenses or ortho-keratology contact lenses in the past 30 days.
- Are an extended contact lens wearer (i.e., sleeping with their contact lenses)
- Are on ongoing atropine treatment for myopia control.
- Have a difference of > 1.0 D in best vision sphere subjective refraction between eyes.
- Have amblyopia and/or strabismus/binocular vision problem.
- Have any known active* ocular disease, allergies and/or infection.
- Have a systemic condition that in the opinion of the investigator may affect a study outcome variable;*
- Are using any systemic or topical medications that in the opinion of the investigator may affect a study outcome variable;*
- Have a known sensitivity to the diagnostic pharmaceuticals to be used in the study.
- Have undergone refractive error surgery or intraocular surgery.
- Are a member of [REDACTED] directly involved in the study.

* For the purposes of this study, active ocular disease is defined as infection or inflammation which requires therapeutic treatment. Mild (i.e. not considered clinically relevant) lid abnormalities (blepharitis, meibomian gland dysfunction, papillae), corneal and conjunctival staining and dry eye are not considered active ocular disease. Neovascularization and corneal scars are the result of previous hypoxia, infection or inflammation and are therefore not active.

* Any potential exclusion will be reviewed with the Principal Investigator or Sub-Investigator prior to final decision making.

7.4 Procedures to Minimize Bias

7.4.1 Labelling and Masking

The Test will be labelled with an investigational label, according to local regulations where the clinical study is being conducted. The investigational label will also include study contact lens coding in order to facilitate investigator masking.

Although approved for use in the country where the clinical study is taking place, the Control contact lenses will be labelled with an investigational label to facilitate masking.

Decoding/Masking Procedures:

The Principal Investigator will be provided, prior to commencing the study, with the masking codes in a sealed envelope and decoding/demasking procedures for use in a medical emergency or where Serious Adverse Events are considered to be related to the Investigative or Control devices.

7.4.2 Randomization procedures

In this crossover study design, each subject will wear the Test contact lens or the Control contact lens first in a bilateral fashion followed by the alternate contact lens. The order of contact lenses will be determined by a predetermined randomization schedule.

7.5 Visit Procedures

Study visits and study visit flow will be per Table 2 and Figure 1 below.

Table 2: Study Visits

Visit number	Visits
1-A	Screening / Baseline Visit
1-B	Pair 1 Dispense
2-A	7 (+3 days) Follow-up Assessment of Pair 1
2-B	Pair 2 Dispense
3-A	7 (+3 days) Follow-up Assessment of Pair 2 and Study Exit

7.5.1 Visit 1A: Baseline Visit

A documented informed consent process will be conducted with all participants prior to their enrollment in the study and prior to any data collection or measurements.

All participants who signed the informed consent/assent letter will be assigned a study ID number. The investigator will determine participant eligibility using the inclusion and exclusion criteria.

Ineligible participants will be discontinued from the study. The procedures to be performed are outlined below.

Visit procedures:

1. The participant is expected to attend the screening visit with their habitual glasses NOT having worn their habitual contact lenses and/or used any rewetting/tear drops from at least one day prior to the study day.
2. The parent (for participants ages 8 to 17) and participant will be required to read and sign a Parental Permission and Assent Form respectively prior to enrollment. This is not applicable to participants aged 18, who will be instead required to read and sign an Informed consent form prior to enrollment. When the parent (for those aged 17 and younger) and participant have signed the necessary forms as stated below, the participant will be considered enrolled in the study.
 - Age 18 - The Participant Informed Consent Form (participant only)
 - Age 12-17 – The Parental Permission Form (participant and parent)
 - Age 8-11 - The Parental Permission Form (parent) and Assent form (participant)
3. Participant demographics and medical history (age, sex, medical conditions, medications, allergies).
4. Contact lens history (habitual contact lens information and wearing habits).
5. [REDACTED]

14. Slit lamp biomicroscopy will be assessed using Efron grading scale as specified in Appendix 2.
15. The investigator will confirm that the participant meets the eligibility specifications set out in the inclusion criteria and exclusion criteria and is eligible to continue in the study.

7.5.2 Visit V1-B: Pair 1 Dispensing

The Screening Visit (V1-A) will be immediately followed by Pair 1 Dispensing Visit (V1-B) on the same day.

Visit procedures:

16. Contact lens Pair #1 will be provided to participants in a manner that does not unmask the participant or investigator as per the randomization schedule in Appendix 3.
17. Participant to open blister packs and apply the Contact lens pair 1 OU – powers matched to vertexed best sphere refraction OU. Allow to settle for 15 minutes.
18. Monocular over-refraction (photopic screen luminance with dim room illumination), change in power (allow 15 min settling time if CL power is changed) if VA is improved by 3 letters.
19. LogMAR visual acuity measurements (with Room light illuminance and screen luminance conditions as specified in Appendix 4):

Mesopic vision (mesopic screen luminance with dim room illumination, after 10 minutes of dark adaptation):

Distance (6m) Low illumination (LI) HC VA; OU (logMAR)

Photopic vision (photopic screen luminance with dim room illumination):

Distance (6m) LIHC VA: OD & OS & OU (logMAR)

Distance (6m) Low room illumination Low contrast (LILC) VA: OU (logMAR)

High contrast near VA (near chart with high room illumination):

Near (40 cm) HIHC VA: OU (logMAR)

22. Review contact lens usage instruction and required wearing time (10 hours per day and 6 days per week) with participants and also with parents/guardians where subjects are 17 years and younger.
23. Dispense Pair 1 lenses. Unmasked staff to apply masked over-labels to sufficient R & L Contact lenses to last until next visit (include at least 2 spare pairs)
24. Schedule for 1-week follow up visit (7 + 3 days from Visit 1)

7.5.3 Visit V2-A: 7 (+3 days) Follow-up Assessment of Pair 1

Visit procedures:

25. The participant will attend the visit having worn study Contact lenses at least 2hrs prior to visit.
26. Review wearing time, problems with CL wear, adverse events, protocol deviations.
27. Unworn Pair 1 (OU) contact lenses will be collected from the subject by the Investigator.

30. LogMAR visual acuity measurements (with Room light illuminance and screen luminance conditions as specified in Appendix 4):

Mesopic vision (mesopic screen luminance with dim room illumination, after 10 minutes of dark adaptation):

Distance (6m) Low illumination (LI) HC VA; OU (logMAR)

Photopic vision (photopic screen luminance dim room illumination):

[figure not shown]
Distance (6m) LIHC VA; OD & OS & OU (logMAR)

Distance (6m) Low room Illumination Low contrast (LILC) VA; OU (logMAR)

High contrast near VA (near chart with high room illumination):

Near (40 cm) HIHC VA; OU (logMAR)

31. Over-refraction (best sphere monocular) distance and monocular photopic screen luminance dim room illumination VA (if any over-refraction)

35. The subject will remove the Pair 1 (OU) study contact lenses worn on the day of Visit 2A, which will be retained and stored in saline solution for return to the Sponsor.

36. Slit lamp biomicroscopy will be assessed using Efron grading scale as specified in Appendix 2.

37. Subjects will undergo washout with saline solution.

7.5.4 Visit V2-B: Pair 2 Dispensing

The Pair 1 follow-up visit (Visit V2-A) will be immediately followed by Pair 2 Dispensing visit (Visit V2-B) on the same day.

Visit procedures:

38. Contact Lens Pair #2 will be provided to participants in a manner that does not unmask the participant or investigator as per the randomization schedule (Appendix 3).

39. Participant to open blister packs and apply the Contact Lens pair 2 OU – powers matched to vertexed best sphere refraction OU. Allow to settle for 15 minutes.

40. Monocular over-refraction (photopic screen luminance with dim room illumination), change in power if VA is improved by 3 letters.

41. LogMAR visual acuity measurements (with room light illumination and screen luminance conditions as specified in Appendix 4):

Mesopic vision (mesopic screen luminance with dim room illumination, after 10 minutes of dark adaptation):

Distance (6m) Low illumination (LI) HC VA; OU (logMAR)

[figure not shown]
Photopic vision (photopic screen luminance with dim room illumination):

Distance (6m) LIHC VA; OD & OS & OU (logMAR)

Distance (6m) Low room Illumination Low contrast (LILC) VA; OU (logMAR)

High contrast near VA (near chart with high room illumination):

Near (40 cm) HIHC VA; OU (logMAR)

44. Review contact lens usage instruction and required wearing time (10 hours per day and 6 days per week) with participants and also with parents/guardians where subjects are 17 years and younger.

45. Dispense Pair 2 contact lenses. Unmasked staff to apply masked over-labels to sufficient R & L Contact lenses to last until next visit (include at least 2 spare pairs).

46. Schedule for 1-week follow up visit (7 + 3 days from Visit 2A)

7.5.5 Visit V3-A: 7 (+3 days) Follow-up Assessment of Pair 2 and Study Exit

47. The participant will attend the visit having worn study Contact lenses for at least 2hrs prior to visit.

48. Review wearing time, problems with CL wear, adverse events, protocol deviations.

49. Unworn Pair 2 (OU) contact lenses will be collected from the subject by the Investigator.

52. LogMAR visual acuity measurements (with Room light illuminance and screen luminance conditions as specified in Appendix 4):

Mesopic vision (mesopic screen luminance with dim room illumination, after 10 minutes of dark adaptation):

Distance (6m) Low illumination (LI) HC VA; OU (logMAR)

Photopic vision (photopic screen luminance dim room illumination):

Distance (6m) LIHC VA; OD & OS & OU (logMAR)

Distance (6m) Low room Illumination Low contrast (LILC) VA; OU (logMAR)

High contrast near VA (near chart with high room illumination):

Near (40 cm) HIHC VA; OU (logMAR)

53. Over-refraction (best sphere monocular) distance and monocular photopic screen luminance dim room illumination VA (if any over-refraction)

57. The subject will remove the Pair 2 (OU) study contact lenses worn on the day of Visit 3A, which will be retained and stored in saline solution for return to the Sponsor.

58. [REDACTED]

59. Slit lamp biomicroscopy will be assessed using [REDACTED]

60. Subjects will undergo washout with saline solution.

7.5.6 Study Exit

Exit visual acuity (LIHC) will be recorded with subjective spherocylindrical refraction result from V1-A refraction (OD & OS & OU (logMAR)). An exit biomicroscopy assessment will be conducted including Fl staining, if participant was fitted with study contact lenses at the screen visit or if biomicroscopy was not completed at a concurrent visit after the screening.

After the exit assessments have been completed, the participant and investigator will complete the study exit and remuneration forms. At this time, the participant will be considered as having exited the study.

When a participant exits the study, the study exit form will be completed. Therefore, this form will be completed either at completion of the study, or if the participant is discontinued from the study at another time. A study exit form must be completed for all participants who have taken a study ID number. If in the opinion of the investigator post-follow-up visits are required, the exit form will be completed after the last follow-up visit.

7.5.7 Summary of Visits and Procedures

Table 3 summarizes the visits and procedures for the study.

Table 3: Summary of Visits and Procedures

Procedures / Data	Visit 1-A	Visit 1-B & 2-B (Dispense)	Visit 2-A & 3-A (Follow Up)	Exit Visit	Unscheduled/ Adverse Events
Visit window	N/A		7 + 3 days	-	N/A
Informed assent/ consent	✓	-	-	-	-
Meet inclusion / exclusion criteria	✓	-	-	-	-
Demographics	✓	-	-	-	-
Presenting VA	✓	-	✓	-	✓
History at baseline	✓	-	-	-	-
History since last visit, including updated medical problems / previous events / treatment	✓	✓	✓	-	✓
Spherical Over-refraction + logMAR VA	✓	✓	✓	-	-
LogMAR VA with CLs	-	✓	✓	-	-
Wear time	-	-	✓	-	*
CL dispense & review wear instructions	-	✓	-	-	*
Compliance assessment / Contact lens and solution returns	-	-	✓	-	*
Slit lamp biomicroscopy: CL assessment worn at visit and ocular assessment	✓	-	✓	✓	✓
Photos / video	*	*	*	-	*
Adverse event assessment	✓	✓	✓	✓	✓
Visit summary	✓	✓	✓	-	✓
* Investigator discretion					
** Related to habitual CLs					

8 Adverse Events

8.1 Adverse Event Definitions

An 'adverse event' refers to any undesirable clinical occurrence in a participant, whether it is considered to be device-related or not. Adverse events (AE) may be classified as 'unanticipated adverse device effects,' 'serious adverse events,' 'significant adverse events,' or 'non-significant adverse events,' as defined below.

Classification	Definition
Serious Adverse Event	Those events that are life-threatening, or result in permanent impairment of a body function, or permanent damage to a body structure or necessitate medical (therapeutic) or surgical intervention to preclude permanent impairment of a body function or permanent damage to a body structure.
Significant Adverse Event	Those non-serious adverse events that occur with contact lens usage that are not sight-threatening but are usually symptomatic and may warrant therapeutic management and /or temporary or permanent discontinuation of contact lens wear.
Non-Significant Adverse Events	Those less severe non-serious adverse events that occur with contact lens usage that are not sight-threatening, may or may not be symptomatic and may warrant palliative management, such as ocular lubricants or temporary interruption of contact lens wear.
Unanticipated Adverse Device Effect	Adverse events in a clinical trial that were not previously identified in the protocol in terms of nature, severity, or degree of incidence. An Unanticipated Serious Adverse Device Effect is an unanticipated adverse event that is serious in nature and caused by or associated with the device and is considered reportable.

AE classification, coding (for reporting to the Sponsor) and examples are provided in the following table of Contact Lens Adverse Event Classification and Reporting table:

Code	Condition	Reporting
Serious Adverse Events		
01	Presumed infectious keratitis or infectious corneal ulcer	Notify Sponsor as soon as possible, within 24 hours ; IRB reporting as per requirements
02	Permanent loss of \geq 2 lines of best spectacle corrected visual acuity (BSCVA)	
03	Corneal injury that results in permanent opacification within central cornea (6mm)	
04	Uveitis or Iritis (e.g. presence of anterior segment inflammation as described in ISO 11980, Annex B)	
05	Endophthalmitis	
06	Hyphema	
07	Hypopyon	
08	Neovascularization within the central 6mm of cornea	
00	Other serious event	
Significant Adverse Events		

11	Peripheral (outside central 6mm), non-progressive, non-infectious ulcer	Notify Sponsor as soon as possible, within 5 working days ; IRB reporting as per requirements
12	Symptomatic corneal infiltrative event	
13	Superior epithelial arcuate lesions (SEALs) involving epithelial split	
14	Corneal staining \geq dense coalescent staining up to 2mm in diameter (e.g. moderate, ISO 11980 grade 3)	
15	Corneal neovascularization \geq 1.0mm vessel penetration (e.g. \geq ISO 11980 Grade 2), if 2 grade change from baseline	
16	Any temporary loss of \geq 2 lines BSCVA for \geq 2wks	
17	Any sign and/or symptom for which subject is administered therapeutic treatment or which necessitates discontinuation of lens wear for \geq 2 weeks	
10	Other significant event	
Non-significant Adverse Events		
21	Conjunctivitis (bacterial, viral or allergic)	Notify Sponsor as soon as possible, within 5 working days ; IRB reporting as per requirements
22	Papillary conjunctivitis if \geq mild scattered papillae/follicles approximately 1mm in diameter (e.g. ISO 11980 Grade 2), if 2 grade change from baseline	
23	Asymptomatic corneal infiltrative events	
24	Any sign and/or symptom for which temporary lens discontinuation for $>$ 1 day is recommended (if not already classified)	
20	Other sign and/or symptom warranting classification as a non-significant adverse event	

Normal or adaptive symptoms

Transient symptoms such as end-of-day dryness, contact lens awareness, itching or burning or other discomfort may occur with contact lens wear and may occasionally reduce wearing time. **These are not reported as adverse events unless in the investigator's opinion they are unexpected in nature, severe or have a high rate of occurrence.**

This clinical study will also ascertain satisfaction or preference with subjective attributes such as comfort, vision, or contact lens handling. Responses to these subjective questionnaires will not be considered as Adverse Events.

8.2 Adverse Events Management

Treatment of an adverse event will depend on its nature and severity. Based on the clinical judgment of the investigator the subject may be referred to an ophthalmologist for treatment.

Expenses incurred for medical treatment as part of study participation will be paid by the Sponsor (bills and prescription receipts kept). The subject must be followed until resolution and an Adverse Event Outcome Form (Appendix 10) completed indicating the course of treatment and resolution of the condition.

8.3 Reporting Adverse Events

An Adverse Event Notification Form (Appendix 10) will be completed for each adverse event. Whenever possible, the adverse event will be photo documented.

All potential Serious and Unanticipated Adverse Device Effects that are related or possibly related to subject participation will be reported to the Principal Investigator and the Sponsor within 24 hours of the investigator becoming aware of the event. The Principal Investigator will report the event to the IRB as soon as possible (by fax, mail/delivery, phone, or email). All fatal or life-threatening events will be reported immediately to the IRB.

Significant and Non-Significant Adverse Events will be reported to the Sponsor as soon as possible, but no later than 5 days after the occurrence.

Sponsor contact details **for adverse events** are:

Contact: Clinical Operations, CooperVision

[REDACTED]

[REDACTED]

[REDACTED]

[REDACTED]

[REDACTED]

[REDACTED]

[REDACTED]

8.4 Discontinuation from the Study

A subject's study participation may be discontinued at any time if, in the opinion of the Sponsor or the investigator, it is in the best interest of the subject. All discontinuations will be fully documented on the appropriate study forms and a discontinuation/exit form will be completed.

9 Device Deficiency Reporting

9.1 Product Defect Reporting (Investigator Responsibility)

Product Defect is the terminology typically used in contact lens products for an *unexpected* observation related to the identity, quality, durability, reliability, or usability of the product under investigation.

NOTE: Observations on study products that are anticipated as a part of the device development process are not considered to be Product Defects or Device Deficiencies.

If the Product Defect is associated with an adverse event, the investigator shall report the Product defect via the Adverse Event Notification Form (Appendix 10).

If the Product Defect is not associated with an adverse event, the investigator shall report the Product Defect via the Clinical Product Defect Notification Case Report Form (Appendix 11).

If the investigator judges that the Product Defect could have led to a Serious Adverse Event if no preventative action was taken, the Product Defect should be reported to the Sponsor via the Product Defect Notification Case Report Form within 24 hours of becoming aware of the defect. The investigator should report to the IRB/EC per their reporting requirements.

All other Product Defects should be reported to CVI as soon as possible, but no later than 5 working days after occurrence.

Sponsor contact details **for Product Defect Notifications** are:

Contact: Clinical Operations, CooperVision
[REDACTED] [REDACTED]
[REDACTED] [REDACTED]
[REDACTED]

9.2 Device Deficiency Reporting (Sponsor Responsibility)

Device Deficiency is defined as the inadequacy of a medical device with respect to its identity, quality, durability, reliability, usability, safety or performance.

The Sponsor will review the Product Defect Notification Case Report Form, gather additional information if needed from the Investigator/CRO and determine whether the notification represents a Device Deficiency. Device Deficiencies will be reported as per Internal CVI procedures.

A summary of Device Deficiencies will be documented in the clinical study report. If no Device Deficiencies are observed in a study, then a statement stating as such will be included in the clinical study report.

10 Statistical Design and Analysis

10.1 Statistical Hypothesis

The primary hypothesis to be tested in this study will be that the binocular high contrast distance visual acuity achieved with [REDACTED] Test contact lenses is non-inferior to that achieved with [REDACTED] Control soft contact lenses.

10.2 Sample Size Calculations

The target sample size for this study is 30 participants to be randomized and to wear both contact lens types. This target was determined based on the sample size calculation below:

to demonstrate non-inferiority in high contrast binocular distance logMAR visual acuity for the Test contact lens compared with the Control contact lens, the sample size estimation is based upon a one-sided paired t-test with $\alpha = 0.025$, $\beta = 0.200$ and a non-inferiority margin of 0.050 logMAR when postulating a true difference of 0.00 logMAR with a standard deviation of 0.07 logMAR a total of 26 participants is required. The target for this study will be for 30 participants to complete the study without a significant protocol deviation.

Therefore, in this study, a maximum of 40 participants may be randomized to achieve a maximum of 30 completed.

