13	Study Costs	38
14	Publication Policy	38
15	References.....	39
17	Appendix 1 – [REDACTED]	40
18	Appendix 2 – [REDACTED]	50
19	Appendix 3 – Randomization.....	51
20	Appendix 4 – [REDACTED]	52
21	Appendix 5 – [REDACTED]	65
22	Appendix 6 – [REDACTED]	65
23	[REDACTED] 7 – [REDACTED]	65
24	Appendix 8 – [REDACTED]	65
25	Appendix 9 – [REDACTED]	65

26 Appendix 10 – Adverse Event Case Report Forms	67
27 Appendix 11 – Clinical Trial Product Defect Notification Form.....	70

1 Study Objective

The objective of this Design Validation clinical investigation is to compare the visual clinical performance of the [REDACTED] investigational contact lens to [REDACTED] contact lenses. CooperVision, Inc. (CVI) is aiming to compare visual acuity and subjective vision ratings of vision quality between two CooperVision lenses: [REDACTED] versus [REDACTED] in habitual soft lens wearers. The [REDACTED] lens is a daily disposable investigational lens in this study (as this lens has not been yet approved or commercially available in the US), the [REDACTED] is commercially available in the US for myopia control.

[figure not shown]
[REDACTED] lens is a silicone hydrogel daily disposable (DD) lens with a similar design to [REDACTED] hydrogel DD lenses. CooperVision, Inc. is interested in comparing visual acuity and subjective vision ratings between these two lenses of different materials to gain insight into the differences between these lenses from this aspect.

The primary outcome variable for this study is:

- High contrast, binocular, distance visual acuity (logMAR) at 1-week visit.

The secondary outcome variable is:

- Subjective vision quality (0-100 scale) at 1-week visit

2 Study Design

This will be a prospective, multiple day, double (investigator and subject) masked, randomized, bilateral crossover study comparing a Test lens against an appropriate Control lens. Each subject will wear the Test lens or the Control lens in a bilateral fashion for 7 days (+ 3 days) followed by the alternate lens for 7 days (+ 3 days). The order of lenses will be randomized.

There will be a total of 3 visits in the study as described in Section 7.5 below.

3 Study Devices and Comparator Products

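### Section 10.2: the stated inputs require 18 participants, not 26; with those inputs 26 gives about 94% power, not 80%

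*Combined protocol and SAP*

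**What the plan says.** The design is a "randomized, bilateral crossover study comparing a Test lens against an appropriate Control lens", so each participant contributes one Test minus Control difference. Section 10.1 makes non-inferiority in binocular high contrast distance acuity the primary hypothesis.

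Section 10.2 sizes the trial for that hypothesis. It says "the sample size estimation is based upon a one-sided paired t-test" with alpha 0.025, beta 0.200 and "a non-inferiority margin of 0.050 logMAR", and it concludes that "when postulating a true difference of 0.00 logMAR with a standard deviation of 0.07 logMAR a total of 26 participants is required". It then adds: "The target for this study will be for 30 participants to complete the study without a significant protocol deviation". Up to 40 may be randomized to reach those 30. The section says that the target of 30 rests on this calculation.

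The section does not say whether 0.07 is the SD of paired differences or of acuity with a single lens. It gives no within-person correlation, and no loss rate is built into the 26.

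**The concern.** One sentence gives every input that a paired sample size calculation needs, together with its result, and the two do not match. The gap is 8 participants, or 44% of the correct figure (8/18), which is too large to be rounding or a software difference.

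The plan derives its target of 30 from this figure, and the cap of 40 follows from the 30. If the inputs are right, the plan overstates the requirement and understates its power. If the 26 is right, an input is wrong or missing, and a reader cannot tell which. The SD matters most, because it is unlabelled and the power of the primary comparison depends on it.

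The true requirement also matters because section 7.3 accepts as few as 10 completers and section 10.4 lets the sponsor stop enrolment after an interim look. How far a smaller trial would fall short depends on which inputs are correct.

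**Working it through.** **Inputs, all from section 10.2:** one-sided alpha 0.025; beta 0.200 (power 80%); margin 0.050 logMAR; true difference 0.00; SD 0.07 logMAR, first taken as the SD of paired differences.

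**1. Normal approximation**

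n = (z₀.₉₇₅ + z₀.₈₀)² × SD² / margin² = (1.960 + 0.842)² × 0.07² / 0.05² = 15.38, so 16.

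**2. Exact paired t-test**

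Power = P(T > t₀.₉₇₅,ₙ₋₁), where T is noncentral t with n − 1 degrees of freedom and noncentrality (0.05/0.07)√n.

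| n | Noncentrality | Critical t | Power |
|---|---|---|---|
| 17 | 2.945 | 2.120 | 79.0% |
| 18 | 3.030 | 2.110 | 81.5% |
| 26 | 3.642 | 2.060 | 93.8% |
| 30 | 3.912 | 2.045 | 96.6% |

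The smallest n with at least 80% power is 18. Using n − 2 degrees of freedom, as in a two-period crossover analysis, also gives 18 (81.2%). The plan's 26 is not reproduced.

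**3. Attempts to reach 26 by changing or adding an input**

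| Variant | Required n |
|---|---|
| One-sided alpha 0.05, 80% power | 14 |
| One-sided alpha 0.0125, 80% power | 22 |
| Two-sided equivalence (two one-sided tests at 0.025), 80% power | 23 |
| Power 90% | 23 |
| Power 95%, exact t | 28 |
| Power 95%, normal approximation | 25.47, so 26 |
| Two independent arms, 80% power | 31 per arm (62 total) |
| SD of differences 0.0857 to 0.0874, 80% power | 26 |
| 18 inflated for a loss above 28% and up to 30.8% | 26 |

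The three routes that give 26 each need something that the plan does not state or that contradicts it. The 95% power route conflicts with the stated beta of 0.200 and uses a normal approximation where a t-test is named. The loss route needs more than the plan's own allowance: (40 − 30)/40 = 25%, and 18/0.75 = 24.

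**4. If 0.07 is the SD for a single lens**

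The SD of differences is then 0.07 × √(2(1 − r)), where r is the within-person correlation. The documents give no r, so a range is shown.

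| r | SD of differences | Required n | Power at 26 | Power at 30 |
|---|---|---|---|---|
| 0 | 0.0990 | 33 | 70% | 76% |
| 0.09 | 0.0944 | 30 | 74% | 80% |
| 0.20 | 0.0885 | 27 | 79% | 85% |
| 0.25 | 0.0857 | 26 | 82% | 87% |
| 0.50 | 0.0700 | 18 | 94% | 97% |

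The required n is 26 for r between about 0.22 and 0.25.

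**5. At the minimum of 10 completers in section 7.3**

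Power is 52% if the SD of differences is 0.07, and about 37% if it is 0.087, a value that would justify 26.

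**The case against.** The strongest reply is that both 18 and 94% depend on reading 0.07 as the SD of paired differences, which section 10.2 does not say. With a single-lens SD and a correlation of about 0.22 to 0.25, 26 would be correct. This stands as a caveat, but it does not rescue the sentence. The named test is paired, so the SD of differences is the natural reading, and the alternative needs a correlation that appears nowhere in the plan.

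The second reply is that little turns on it. The target of 30 exceeds both 18 and 26. Even on the single-lens reading, power at 30 drops below 80% only if the correlation is under about 0.09, which would be low for two acuity measurements on the same person, although the documents give no value. This is fair and limits the weight of the point: the finding is not that the trial is underpowered.

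Rounding of the inputs has also been considered. Taking a true difference of 0.005, a margin of 0.0495 and an SD of 0.075, all at the unfavourable ends of their rounding ranges, the required n is 25, so rounding alone does not produce 26. Nor does any redaction fall within the calculation.

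**Conclusion.** The concern holds. Under the inputs stated in section 10.2, the required number is 18, not 26, and 26 corresponds to a beta of about 0.06 (1 − 0.938), not 0.200. No variant that keeps all the stated inputs gives 26. The figures of 18, 93.8% and 96.6% assume that 0.07 is the SD of paired differences and that the true difference is zero.

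On that reading the error is conservative and 30 completers are more than enough. What remains is that the calculation behind the target cannot be reproduced from what is written, and the definition of its key input is missing. This should be fixed, but it does not threaten the trial if 30 complete and the direct reading is right.

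**What to change.** Restate section 10.2 so that inputs and result agree, and say explicitly that the SD is that of paired Test minus Control differences. There are two ways to do this:

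- **If the inputs are right:** state that 18 participants are required for 80% power and that 30 completers give about 97%.
- **If the 26 is right:** state the input that produced it. The sponsor should check the SD of differences (about 0.087 would give 26, with 80.4% power), a single-lens SD with its correlation, any loss allowance, and whether beta was really 0.05 with a normal approximation. The power at 30 should then be given for that input.

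The cost is one corrected sentence. On the direct reading no participants are added, and the target of 30 and the cap of 40 can stay.
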